10.3.2.2 Analytical Approach

The number of participants, mean, median, standard deviation (SD), minimum, and maximum values will be presented at each scheduled visit that the variable is recorded. The following visits should be presented unless otherwise stated: Baseline, 207 week 4, 8, 12, 16 (labelled as “207 / Week X”) and 208 week 4, 8, 12, 16, 24, 36 and 40 (labelled as “208 / Week X”).

As ADCT scores were not collected at week 8 during the 207 parent study they will not be summarised at these visits.

Figures for the mean percentage change and change from baseline for ADCT score will be displayed over time. Waterfall plots for the percentage change and change from baseline will also be produced for the same visits as presented in tables.

For the daily PP-NRS and SD-NRS endpoints, only graphical summaries will be presented.

10.3.3 Responder Analysis

10.3.3.1 Estimands

The exploratory response endpoints are:

- Achievement of 50% reduction in each of the four region scores of the EASI
- Change in response states from Day -1 to weeks 8, 16, 24 and 36. Response states will be defined using the EASI score percentage change from baseline with categories for: $\geq 25\%$ increase, no change (<25% increase to <25% decrease), 25% to <50% decrease, 50% to <75% decrease, 75% to <90% decrease, $\geq 90\%$ decrease

Achievement of 50% reduction in each of the four region scores of the EASI

The population summary measure of interest will be the percentage of participants achieving response at each visit.

Change in response states from Day -1 to weeks 8, 16, 24 and 36

The population summary measure of interest will be the percentage of participants with each change in response state.

Intercurrent events will be accounted for in the following manner:

Table 7: Intercurrent Event Strategies of the 50% reduction of EASI in body regions

Use of TCS/TCI rescue medications within 4 weeks or type 1 prohibited meds from 207, use at any time of other prohibited medications for atopic dermatitis	Treatment discontinuation, non-compliance with treatment, other deviations from the protocol
Composite strategy Participants will be considered as ‘non-responders’ 1) within 4 weeks after the use of TCS/TCI rescue medications or type 1 prohibited meds from 207 2) at any time after the use of other prohibited medications for atopic dermatitis	Treatment policy strategy: Data will be used as collected

Data point set DPS4b will be used for exploratory response endpoints.

10.3.3.2 Analytical Approach

Summary tabulations of frequency and percentage of participants within each category will be presented at each scheduled visit that the variable is recorded. The following visits should be presented unless otherwise stated: Baseline, 207 Week 4, 8, 12, 16 (labelled as “207 / Week X”) and 208 week 4, 8, 12, 16, 24, 36, 40 (labelled as “208 / Week X”).

Plots for the mean percentage change and change from baseline in EASI score over time by region will be produced along with waterfall plots for the percentage change and change from baseline in EASI score. The proportion of participants achieving 50% reduction in EASI score over time by region will also be displayed.

11 Safety Analyses

The FAS or the parent study specific FAS for the study/cohort specific analysis will be used for all Safety estimands and summaries. A treatment policy approach will be used for all safety estimands, including all data collected regardless of treatment discontinuation, treatment compliance and use of other medications. All safety endpoints will be listed.

11.1 Early Stopping

In the event that the study is stopped early and only a reduced amount of outputs are needed, safety data will only be reported for the period beginning with the first dose of active IMP in this study.

Additionally to the primary safety endpoints, only the non-serious TEAEs will be summarized by SOC and PT, however, PTs will be presented only in case of TEAEs reported by at least 5% of participants in any treatment group.

Data will be presented as collected, no imputations or data exclusion will be made.

The list of outputs produced in the case the study is stopped early are provided in 16Appendix 1: List of Tables, Figures and Listings.

11.2 Extent of Exposure

The duration of exposure (days) and number of doses taken will be summarized using summary statistics for continuous data. Two summary tables will be produced, one for the duration of exposure from first dose in this study and one from the first dose of active treatment across this study and the parent study.

For the 208 specific summary the number and percentage of participants with at least 4, 8, 12, 16, 24 and 36 weeks (28, 56, 84, 112, 168, 252 days respectively) of exposure will also be presented.

For the 208 and parent study summary the number and percentage of participants with at least 16, 20, 24, 28, 32, 40 and 52 weeks (112, 140, 168, 196, 224, 280, 364 days respectively) of exposure will also be presented.

The total exposure per 100 patient-years will also be summarised for each treatment group for both summaries.

Treatment start and stop dates, exposure duration (days), number of doses administered, number of capsules taken and reasons for dose adjustments and dose interruptions will be listed by participant.

11.3 Adverse Events

In this study adverse events will be reported from the date of signed informed consent and through the Week 36 visit up to 30 days after the last dose of IMP. Adverse events occurring after 30 days post-treatment would only be reported if the investigator considers it to be related to the study treatment.

AEs reported during the parent study that are ongoing at the end of treatment visits will continue to be followed up in this study until resolution or the participant completes the study, whichever is first.

Two summaries will be produced for each classification of adverse events. One will use DPS1 and report only those adverse events that started during this study until 30 days after the last dose of IMP and one that will use DPS2 and report those adverse events that occur following the first dose of active IMP, either in the parent study or in this study until 30 days after the last dose of IMP in this study.

Only treatment emergent AEs (TEAEs) will be included in the summaries, pre-treatment AEs will be included in the listings of all AEs.

All AEs will be coded using MedDRA. The dictionary will be updated through the life of the study with version 24.0 used initially. Severity of event will be coded using the Common Terminology Criteria for Adverse Events (CTCAE) v5.0.

In addition to the primary AE summary specified in Section 9, TEAEs will be summarized by system organ class (SOC) and preferred term (PT) for each of the reporting periods. For the period defined by this study only, the number and percentage of participants reporting events, and the number and rate per 100 patient-years of events will be presented. For the summary looking at the period defined since first dose of active IMP by either in this study and the relevant parent study, the number and percentage of participants reporting events, and the number and rate per 100 patient-years of events will be presented.

For the incidence statistics, a participant who has multiple events in the same SOC or the same preferred term will be counted only once. All events will be counted in the number and rate per 100 years statistics. Adverse event summaries will be sorted by the internationally agreed SOC order (Table 10) and decreasing incidence of preferred term within SOC in the total column.

Related TEAEs, TEAEs of Grade 3 or above, serious TEAEs and TEAEs leading to discontinuation of study drug will also be summarised by SOC and PT in the manner described above.

Non-serious TEAEs will be also summarized by SOC and PT, however, PTs will be presented only in case of TEAEs reported by at least 5% of participants in any treatment group.

11.4 Deaths, Serious Adverse Events and other Significant Adverse Events

Serious AEs, fatal AEs and AEs leading to discontinuation of study drug will each be listed separately by participant.

No specific adverse events are considered to be of special interest for EDP1815.

11.5 Pregnancies

Pregnancy test data will be listed only.

11.6 Clinical Laboratory Evaluations

Central laboratory data will be used for all safety laboratory evaluations. Table 11 shows the parameters which will be collected and the units in which they will be supplied. Lab data will be transformed as appropriate to the International System of Units (SI units) as part of the SDTM programming and SI units will be used for all summaries.

Haematology and chemistry parameters will be summarized by visit, including change from baseline for all post-baseline visits, using DPS3.

The number and percentage of participants showing shifts from baseline to worst-case post-baseline with respect to the normal ranges will also be summarized for each haematology and chemistry parameter, using DPS1. Categories will be:

- Low
- Normal
- High

Haematology and chemistry values will also be flagged for potentially clinically important (PCI) values if they meet any of the criteria for Grade 2 or higher events according to CTCAE V5.0. The PCI criteria are listed in Table 11. The number and percentage of participants showing shifts from baseline to worst-case baseline with respect to PCI criteria will be summarized for all parameters where PCI criteria have been defined, using DPS1. Categories will be:

- Low
- Within range
- High

For both the normal range and PCI summaries, the determination of worst-case post-baseline will consider both scheduled and unscheduled assessments which occur after the first dose of study treatment. Percentages will use the number of participants with at least one post-baseline assessment available as the denominator. If the baseline value is missing it will be assumed to be normal/within range. Worst-case can be either High or Low and if a participant has post-baseline values both above and below the normal range/PCI criteria then they will be counted in both relevant categories.

Haematology and chemistry data will be listed, including changes from baseline, normal ranges, flags for measurements outside the normal range, and flags for meeting PCI criteria. In addition, for participants who meet at least one PCI criteria, all values within the laboratory type (haematology or chemistry) will be listed separately.

Urinalysis data will be listed only.

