14.4. Toxicity Grading Scale

The following scales come from the FDA Guidance for Industry *Toxicity Grading Scale for Healthy Adult and Adolescent Volunteers Enrolled in Preventive Vaccine Clinical Trials*, September 2007.

Temperature Adverse Event Grading Scale

Vitals Signs*	Mild (Grade 1)	Moderate (Grade 2)	Severe (Grade 3)	Potentially Life Threatening (Grade 4)
Fever (°C)**	38.0 – 38.4	38.5 – 38.9	39.0 – 40	> 40
(°F)**	100.4 – 101.1	101.2 – 102.0	102.1 - 104	>104

Laboratory Results Adverse Event Grading Scale

Serum *	Mild (Grade 1)	Moderate (Grade 2)	Severe (Grade 3)	Potentially Life Threatening (Grade 4)**
Sodium – Hyponatremia mEq/L	132 – 134	130 – 131	125 – 129	< 125
Sodium – Hypermnatremia mEq/L	144 – 145	146 – 147	148 – 150	> 150
Potassium – Hyperkalemia mEq/L	5.1 – 5.2	5.3 – 5.4	5.5 – 5.6	> 5.6
Potassium – Hypokalemia mEq/L	3.5 – 3.6	3.3 – 3.4	3.1 – 3.2	< 3.1
Glucose – Hypoglycemia mg/dL	65 – 69	55 – 64	45 – 54	< 45
Glucose – Hyperglycemia				Insulin requirements or hyperosmolar coma
Fasting – mg/dL	100 – 110	111 – 125	>125	
Random – mg/dL	110 – 125	126 – 200	>200	
Blood Urea Nitrogen BUN mg/dL	23 – 26	27 – 31	> 31	Requires dialysis
Creatinine – mg/dL	1.5 – 1.7	1.8 – 2.0	2.1 – 2.5	> 2.5 or requires dialysis
Calcium – hypocalcemia mg/dL	8.0 – 8.4	7.5 – 7.9	7.0 – 7.4	< 7.0
Calcium – hypercalcemia mg/dL	10.5 – 11.0	11.1 – 11.5	11.6 – 12.0	> 12.0
Magnesium – hypomagnesemia mg/dL	1.3 – 1.5	1.1 – 1.2	0.9 – 1.0	< 0.9
Phosphorous – hypophosphatemia mg/dL	2.3 – 2.5	2.0 – 2.2	1.6 – 1.9	< 1.6
CPK – mg/dL	1.25 – 1.5 x ULN***	1.6 – 3.0 x ULN	3.1 – 10 x ULN	> 10 x ULN
Albumin – Hypoalbuminemia g/dL	2.8 – 3.1	2.5 – 2.7	< 2.5	--
Total Protein – Hypoproteinemia g/dL	5.5 – 6.0	5.0 – 5.4	< 5.0	--
Alkaline phosphate – increase by factor	1.1 – 2.0 x ULN	2.1 – 3.0 x ULN	3.1 – 10 x ULN	> 10 x ULN
Liver Function Tests –ALT, AST increase by factor	1.1 – 2.5 x ULN	2.6 – 5.0 x ULN	5.1 – 10 x ULN	> 10 x ULN
Bilirubin – when accompanied by any increase in Liver Function Test increase by factor	1.1 – 1.25 x ULN	1.26 – 1.5 x ULN	1.51 – 1.75 x ULN	> 1.75 x ULN
Bilirubin – when Liver Function Test is normal; increase by factor	1.1 – 1.5 x ULN	1.6 – 2.0 x ULN	2.0 – 3.0 x ULN	> 3.0 x ULN
Cholesterol	201 – 210	211 – 225	> 226	---
Pancreatic enzymes – amylase, lipase	1.1 – 1.5 x ULN	1.6 – 2.0 x ULN	2.1 – 5.0 x ULN	> 5.0 x ULN

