* The laboratory values provided in the tables serve as guidelines and are dependent upon institutional normal parameters. Institutional normal reference ranges should be provided to demonstrate that they are appropriate.

** The clinical signs or symptoms associated with laboratory abnormalities might result in characterization of the laboratory abnormalities as Potentially Life Threatening (Grade 4). For example, a low sodium value that falls within a grade 3 parameter (125-129 mEq/L) should be recorded as a grade 4 hyponatremia event if the subject had a new seizure associated with the low sodium value.

***ULN” is the upper limit of the normal range.

Hematology *	Mild (Grade 1)	Moderate (Grade 2)	Severe (Grade 3)	Potentially Life Threatening (Grade 4)
Hemoglobin (Female) - gm/dL	11.0 – 12.0	9.5 – 10.9	8.0 – 9.4	< 8.0
Hemoglobin (Female) change from baseline value - gm/dL	Any decrease – 1.5	1.6 – 2.0	2.1 – 5.0	> 5.0
Hemoglobin (Male) - gm/dL	12.5 – 13.5	10.5 – 12.4	8.5 – 10.4	< 8.5
Hemoglobin (Male) change from baseline value – gm/dL	Any decrease – 1.5	1.6 – 2.0	2.1 – 5.0	> 5.0
WBC Increase - cell/mm ³	10,800 – 15,000	15,001 – 20,000	20,001 – 25,000	> 25,000
WBC Decrease - cell/mm ³	2,500 – 3,500	1,500 – 2,499	1,000 – 1,499	< 1,000
Lymphocytes Decrease - cell/mm ³	750 – 1,000	500 – 749	250 – 499	< 250
Neutrophils Decrease - cell/mm ³	1,500 – 2,000	1,000 – 1,499	500 – 999	< 500
Eosinophils - cell/mm ³	650 – 1500	1501 - 5000	> 5000	Hypereosinophilic
Platelets Decreased - cell/mm ³	125,000 – 140,000	100,000 – 124,000	25,000 – 99,000	< 25,000
PT – increase by factor (prothrombin time)	1.0 – 1.10 x ULN**	1.11 – 1.20 x ULN	1.21 – 1.25 x ULN	> 1.25 ULN
PTT – increase by factor (partial thromboplastin time)	1.0 – 1.2 x ULN	1.21 – 1.4 x ULN	1.41 – 1.5 x ULN	> 1.5 x ULN
Fibrinogen increase - mg/dL	400 – 500	501 – 600	> 600	--
Fibrinogen decrease - mg/dL	150 – 200	125 – 149	100 – 124	< 100 or associated with gross bleeding or disseminated intravascular coagulation (DIC)

* The laboratory values provided in the tables serve as guidelines and are dependent upon institutional normal parameters. Institutional normal reference ranges should be provided to demonstrate that they are appropriate.

** “ULN” is the upper limit of the normal range.

Urine *	Mild (Grade 1)	Moderate (Grade 2)	Severe (Grade 3)	Potentially Life Threatening (Grade 4)
Protein	Trace	1+	2+	Hospitalization or dialysis
Glucose	Trace	1+	2+	Hospitalization for hyperglycemia

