21	Congenital, familial and genetic disorders
22	General disorders and administration site conditions
23	Investigations
24	Injury, poisoning and procedural complications
25	Surgical and medical procedures
26	Social circumstances
27	Product issues

24 Appendix 11: Safety Laboratory Evaluations

Table 11: Safety Laboratory Parameters and Units

Category	Parameter	Conventional Unit	SI Units	PCI Criteria (SI units)	
				Low	High
Haematology	Hemoglobin	g/dL	g/L	<100 ≥20 decrease from BL	>20 increase from BL
	Hematocrit	%	L/L		
	Red blood cell count	10 ⁶ /uL	10 ¹² /L		
	White blood cell count	10 ³ /uL	10 ⁹ /L	<3	
	Platelet count	10 ³ /uL	10 ⁹ /L	<75	
	Mean corpuscular volume	fL	fL		
	Mean corpuscular hemoglobin	pg	pg		
	Mean corpuscular hemoglobin concentration	g/dL	g/L		
	Absolute neutrophils	10 ³ /uL	10 ⁹ /L	<1.5	
	Absolute lymphocytes	10 ³ /uL	10 ⁹ /L	<0.8	>4
	Absolute monocytes	10 ³ /uL	10 ⁹ /L		
	Absolute eosinophils	10 ³ /uL	10 ⁹ /L		
	Relative neutrophils	%	%		
	Relative lymphocytes	%	%		
	Relative monocytes	%	%		
	Relative eosinophils	%	%		
	Relative reticulocytes	%	%		

Category	Parameter	Conventional Unit	SI Units	PCI Criteria (SI units)	
				Low	High
Chemistry	Aspartate aminotransferase (AST)	U/L	U/L		>3xULN if BL did not exceed ULN, >3xBL if BL was above ULN
	Alanine aminotransferase (ALT)	U/L	U/L		>3xULN if BL did not exceed ULN, >3xBL if BL was above ULN
	Creatinine	mg/dL	mcmol/L		>1.5xULN if did not exceed ULN, >1.5xBL if BL was above ULN
	Potassium	mEq/L	mmol/L		>5.5
	Sodium	mEq/L	mmol/L	<125	>150
	Blood urea nitrogen	mg/dL	mmol/L		
	Total bilirubin	mg/dL	mcmol/L		>1.5xULN if BL did not exceed ULN, >1.5xBL if BL was above ULN
	C-Reactive Protein (CRP)	mg/L	nmol/L		
	Gamma-glutamyl transpeptidase	U/L	U/L		

Category	Parameter	Conventional Unit	SI Units	PCI Criteria (SI units)	
				Low	High
Urinalysis	Protein	mg/dL	mg/dL		
	Blood				
	Glucose	mg/dL	mg/dL		
	Ketones	mg/dL	mg/dL		
	Bilirubin				
	pH	pH	pH		
	Nitrites				
	Specific gravity				

BL=Baseline, PCI = potentially clinically important, ULN = Upper limit of normal range.

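### SAP Table 11 gives potassium no low PCI cut-off, although section 11.6 defines laboratory PCI as CTCAE v5.0 Grade 2 or higher; the low sodium cut-off should be checked at the same time (low priority)

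*SAP*

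**What the plan says.** SAP 11.6 sets one rule for haematology and chemistry: values are "flagged for potentially clinically important (PCI) values if they meet any of the criteria for Grade 2 or higher events according to CTCAE V5.0". It adds that "The PCI criteria are listed in Table 11", so Table 11 (SAP Appendix 11) is what a programmer will code.

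The two electrolyte rows of Table 11 read as follows:

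- Potassium: "Potassium mEq/L mmol/L >5.5". The single limit is in the High column and the Low cell is empty.
- Sodium: "Sodium mEq/L mmol/L <125 >150", that is, Low <125 and High >150.

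For every parameter with PCI criteria, 11.6 then summarises shifts from baseline to worst case in three categories: Low, Within range and High. A separate listing covers participants with at least one PCI value. Worst-case change against PCI criteria for laboratory parameters is a secondary safety endpoint in SAP 4.2.

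The same section provides a second, independent route. Shifts "with respect to the normal ranges will also be summarized for each haematology and chemistry parameter, using DPS1" are planned, and the listings carry "flags for measurements outside the normal range, and flags for meeting PCI criteria".

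**The concern.** The text and the table it cites do not say the same thing. Potassium has a PCI criterion, so it enters the three-category shift table, but its Low category can never be filled. Someone who reads 11.6 and then sees no participant in that category would conclude that nobody had a Grade 2 or higher low potassium. In fact the table could not have shown one.

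For sodium the question is whether <125 is really the Grade 2 limit or belongs to a more severe grade. If it is more severe, the shift table would understate low sodium in the same way, though not completely.

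What is at stake is a secondary safety endpoint in a study whose primary objective is safety. The primary adverse event endpoint does not use the PCI flag.

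**Working it through.** No sample size, power or error rate is involved. The check applies the Table 11 rules to a range of values and compares the results with the only grading scale printed in the documents.

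**Inputs**

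- Table 11, in mmol/L: potassium PCI High if >5.5, otherwise Within range. Sodium PCI Low if <125, High if >150, otherwise Within range.
- Protocol 14.4, in mEq/L (equal to mmol/L for these two ions). The row "Potassium – Hypokalemia mEq/L" gives Grades 1 to 4 as 3.5-3.6, 3.3-3.4, 3.1-3.2 and <3.1. The low sodium row gives 132-134, 130-131, 125-129 and <125.
- Protocol 9.4.2: 14.4 is used only for temperature and laboratory results that CTCAE v5.0 does not cover. The CTCAE v5.0 limits are not in either document.

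**Low side**

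| Value (mmol/L) | Table 11 PCI class | Grade on 14.4 |
|---|---|---|
| Potassium 3.5-3.6 | Within range | 1 |
| Potassium 3.3-3.4 | Within range | 2 |
| Potassium 3.1-3.2 | Within range | 3 |
| Potassium 2.4-3.0 (lowest tested 2.4) | Within range | 4 |
| Sodium 132-134 | Within range | 1 |
| Sodium 130-131 | Within range | 2 |
| Sodium 125-129 | Within range | 3 |
| Sodium 122-124 (lowest tested 122) | Low | 4 |

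Against 14.4, Table 11 flags none of the three potassium bands at Grade 2 or higher and one of the three sodium bands. The Grade 1 potassium band does not count against it, because a Grade 2 rule would leave it unflagged anyway.

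**Is 14.4 a fair yardstick?** The high side tests this:

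| Value (mmol/L) | Table 11 PCI class | Grade on 14.4 |
|---|---|---|
| Potassium 5.3-5.4 | Within range | 2 |
| Potassium 5.5 | Within range | 3 |
| Sodium 146-147 | Within range | 2 |
| Sodium 148-150 | Within range | 3 |

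Table 11 does not follow 14.4 on the high side either, so 14.4 was not its source. It can show that a cut-off deserves checking, but not that the cut-off departs from CTCAE v5.0.

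**What follows for each electrolyte**

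- Potassium: the argument does not depend on where a limit lies. An empty cell implements no limit at all. It can match the Grade 2 or higher rule only if CTCAE v5.0 contains no low-potassium criterion at that level that a laboratory value could meet.
- Sodium: there is a limit, and whether it is the right one depends on CTCAE figures that the documents do not give. The footnote to 14.4 speaks of "a low sodium value that falls within a grade 3 parameter (125-129 mEq/L) should be recorded as a grade 4 hyponatremia event", but the sentence goes on to require an associated new seizure. It confirms that 125-129 is Grade 3 on that scale and does not make such values Grade 4 in general.

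**Which outputs are affected.** They are Table 14.3.4.2.3 and Listing 16.2.7.2.4. A participant with another chemistry PCI value would still have all chemistry results listed, potassium included. SAP Table 9 records early termination with reduced safety output, and the Early Stop column of SAP Appendix 1 marks both outputs No.

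**The case against.** The strongest objection is that the rule said to be breached cannot be seen. Section 11.6 refers to CTCAE v5.0, its limits are not printed, and 14.4 is a fallback scale that Table 11 visibly does not follow. This stands for sodium. A reader might infer that sodium of 125-129 is wrongly missed, but the documents do not support that as a finding. It does not remove the potassium point, which concerns a missing limit and not a misplaced one.

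A reader might also infer that low potassium and sodium of 125-129 are never flagged anywhere. That is not so. Values below the laboratory's lower limit still get the normal-range flag and count in the normal-range shift table, and Protocol 9.10 has clinically significant results recorded as adverse events. Nor is every low potassium a missed PCI value, since Grade 1 values fall outside the rule.

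Finally, both affected outputs are marked as not produced, so the defect may change no reported result. This largely stands, with two qualifications. SAP 16.3 says that after an early stop the safety outputs follow the full plan, which conflicts with its own Early Stop column. That column also drops the normal-range chemistry shift table and the chemistry listing, leaving adverse event reporting as the remaining route in the reduced package.

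**Conclusion.** The point holds in a narrow form. For low potassium, Table 11 does not implement the rule stated in 11.6: followed as written, it puts every low value, however extreme, in the Within range category of the PCI shift table. For low sodium, <125 is a cut-off to verify and not a demonstrated error.

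The number of participants affected cannot be estimated, because the sample size is left open and no laboratory frequencies are given. With the Early Stop column in force, the effect on reported results is nil and the priority is low. If the sentence in SAP 16.3 were to govern, the flag would be used and the point would matter more.

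Two assumptions carry the conclusion. The first is that CTCAE v5.0 has at least one low-potassium criterion at Grade 2 or higher that can be judged from a laboratory value. The second is that the empty Low cell is genuine and not a loss in text extraction; the columns in the potassium and sodium rows are consistent, which supports that reading.

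**What to change.** Reconcile the Low potassium and Low sodium cells of Table 11 with the CTCAE v5.0 limits for Grade 2 or higher, and check the remaining cells against the same source. If another grade was intended for some parameters, say so in 11.6. The SAP already uses Grade 3 or above for QTcF and vital signs in 11.7, so a parameter-specific grade would not be out of place, but it must be stated. Where a cell is left empty on purpose, add a short note giving the reason.

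Also settle whether the sentence in SAP 16.3 or the Early Stop column governs, since that decides whether the PCI flag is used at all.

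The cost is a review of one table, a small change to the flag derivation and a rerun on central laboratory data. The downside is a few more flagged values. No new data are needed.
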